15.6.3 Pregnancy Test

Pregnancy testing (serum β -HCG) will be performed at screening and 30 days post treatment. A listing will display all the results as presented in “Pregnancy Test” eCRF page.

16 Analyses of Other Endpoints

16.1 Pharmacokinetics

Population: PK Analysis Set

Pharmacokinetic parameters will be calculated by the Clinical PK/Pd Group of QP, Merck, Darmstadt, Germany, or by a clinical research organization selected by the sponsor, using standard non-compartmental methods and the actual administered dose. Pharmacokinetic parameters will be calculated using the actual elapsed time since dosing, given with a precision of 15 significant digits or the SAS format Best12. In cases where the actual sampling time is missing, calculations will be performed using the scheduled time. Otherwise, there will be no further imputation of missing data.

Missing concentrations (e.g. no sample, insufficient sample volume for analysis, no result or result not valid) will be reported and used generally as “N.R.”.

PK concentrations which are erroneous due to a protocol violation (as defined in the CSP), sampling processing or analytical error (as documented in the bioanalytical report) may be excluded from the PK analysis, if agreed by the sponsor. In this case the rationale for exclusion must be provided in the CSR. Any other PK concentrations that appear implausible to the clinical pharmacologist/clinical PK/Pd scientist will not be excluded from the analysis. Any implausible data will be documented in the CSR.

The following PK parameters will be calculated from peposertib and peposertib metabolite (M467) plasma concentrations for fraction day (FD) FD1 and/or FD9 as indicated. Appropriate adjustments will be made for differences in molecular weight (MW) (peposertib MW = 481.92 gmol⁻¹; metabolite M467 MW = 467.12 gmol⁻¹).

C_{max}	Maximum observed concentration
$C_{max}/Dose$	The dose-normalized C_{max} . Normalized using the formula $C_{max}/Dose$.
t_{max}	The time to reach C_{max} during a dosing interval (unless otherwise defined, the first occurrence is taken if multiple/identical C_{max} values)
AUC_{0-t}	The area under the curve (AUC) from time 0 (dosing time) to the last sampling time at which the concentration is at or above the lower limit of quantification (LLOQ). Calculated using the mixed log linear trapezoidal rule (linear up, log down)
AUC_{0-24}	The AUC from time 0 (dosing time) to 24 hours postdose. AUC_{0-24} will be based on the estimated concentration at 24 hours, and not the concentration at the actual observation time. Calculated using the mixed log linear trapezoidal rule (linear up, log down)
$AUC_{0-\infty}$	The AUC from time 0 (dosing time) to infinity based on the predicted value for the concentration at t_{last} , as estimated using the linear regression from λ_z determination for FD1. Calculated using the mixed log linear trapezoidal rule (linear up, log down). $AUC_{0-\infty} = AUC_{0-t} + C_{last\ pred}/\lambda_z$
$AUC_{0-t}/Dose$	The dose-normalized AUC_{0-t} . Normalized using the formula $AUC_{0-t}/Dose$.
$AUC_{0-24}/Dose$	The dose-normalized AUC_{0-24} . Normalized using the formula $AUC_{0-24}/Dose$.
$AUC_{0-\infty}/Dose$	The dose-normalized $AUC_{0-\infty}$. Normalized using the formula $AUC_{0-\infty}/Dose$.
$AUC_{extra\%}$	The AUC from time t_{last} extrapolated to infinity given as percentage of $AUC_{0-\infty}$, $AUC_{extra\%} = (\text{extrapolated area}/AUC_{0-\infty}) * 100$ for FD1
$t_{1/2}$	Apparent terminal half-life, $t_{1/2} = \ln 2/\lambda_z$
CL/f	Apparent total body clearance of drug, calculated as Dose/ $AUC_{0-\infty}$ (predicted) for FD1 for peposertib only
V_z/f	Apparent volume of distribution during the terminal phase following extravascular administration for peposertib only. $V_z/f = \text{Dose}/(AUC_{0-\infty} * \lambda_z)$ for FD1 and $V_z/f = \text{Dose}/(AUC_{0-24} * \lambda_z)$ for FD9

CLss/f	The apparent total body clearance at steady state following extravascular administration, taking into account the fraction of dose absorbed. Calculated by Dose/AUC ₀₋₂₄ for FD9 for peposertib only
R _{acc} (C _{max})	The accumulation factor to assess the increase in maximum concentration from FD1 to FD9 R _{acc} (C _{max}) = (C _{max} FD9)/(C _{max} FD1) for peposertib and M467
R _{acc} (AUC ₀₋₂₄)	The accumulation factor to assess the increase in exposure from FD1 to FD9 during time 0 to 24 hours. R _{acc} (AUC ₀₋₂₄) = (AUC ₀₋₂₄ FD9)/(AUC ₀₋₂₄ FD1) for peposertib and M467
MR _{AUC0-t}	Metabolic ratio of AUC _{0-t} . AUC _{0-t} for M467 divided by the AUC _{0-t} of peposertib corrected for MW: MR _{AUC0-t} *481.92/467.12
MR _{AUC0-24}	Metabolic ratio of AUC ₀₋₂₄ . AUC ₀₋₂₄ for M467 divided by the AUC ₀₋₂₄ of peposertib corrected for MW: MR _{AUC0-24} *481.92/467.12
MR _{AUC0-∞}	Metabolic ratio of AUC _{0-∞} for FD1 only. AUC _{0-∞} for M467 divided by the AUC _{0-∞} of peposertib corrected for MW: MR _{AUC0-∞} *481.92/467.12
MR _{C_{max}}	Metabolic ratio of C _{max} . C _{max} for M467 divided by the C _{max} of peposertib corrected for MW: MR _{C_{max}} *481.92/467.12

The following PK parameters will be calculated from capecitabine and its metabolite (5-fluorouracil) plasma concentrations for FD1 and/or FD9 as indicated.

C _{max}	Maximum observed concentration
t _{max}	The time to reach C _{max} during a dosing interval (unless otherwise defined, the first occurrence is taken if multiple/identical C _{max} values)
t _{last}	The time at which last quantifiable concentration occurs.
AUC _{0-t}	The area under the curve (AUC) from time 0 (dosing time) to the last sampling time at which the concentration is at or above the LLOQ. Calculated using the mixed log linear trapezoidal rule (linear up, log down)
AUC _{0-∞}	The AUC from time 0 (dosing time) to infinity based on the predicted value for the concentration at t _{last} , as estimated using the linear regression from λ _z determination for FD1. Calculated using the mixed log linear trapezoidal rule (linear up, log down). AUC _{0-∞} =AUC _{0-t} +C _{last pred} /λ _z

AUC _{extra%}	The AUC from time t_{last} extrapolated to infinity given as percentage of AUC _{0-∞} , AUC _{extra%} = (extrapolated area/AUC _{0-∞})*100 for FD1
$t_{1/2}$	Apparent terminal half-life, $t_{1/2} = \ln 2/\lambda_z$
CL/f	Apparent total body clearance of drug, calculated as Dose/AUC _{0-∞} (predicted) for FD1 for capecitabine only
V_z/f	Apparent volume of distribution during the terminal phase following extravascular administration. $V_z/f = \text{Dose}/(\text{AUC}_{0-∞} * \lambda_z)$ for FD1 for capecitabine only

The following PK parameters will be calculated for diagnostic purposes and listed:

- Apparent terminal rate constant (λ_z).
- First (λ_z low) and last (λ_z upp) time point of the time interval of the log-linear regression to determine λ_z .
- Number of data points (N) included in the log-linear regression analysis to determine λ_z .
- Goodness-of-fit statistic (Rsq,adj) for calculation of λ_z .

Concentrations below the LLOQ at any point in the profile will be taken as zero for calculating the AUC. Predose samples that occur before the first drug administration will be assigned a time of 0 hours, as if the sample had been taken simultaneously with the study drug administration. The same applies to predose samples during multiple dosing.

The regression analysis for λ_z will contain data from at least 3 different time points in the terminal phase consistent with the assessment of a straight line on the log-transformed scale. Phoenix WinNonlin best fit methodology will be used as standard. However, in some cases, further adjustment may be made by the pharmacokineticist, if warranted, and reviewed by the Sponsor. The last quantifiable concentration will always be included in the regression analysis, while the concentration at t_{max} and any concentrations below the LLOQ which occur after the last quantifiable data point will not be used.

If AUCextra% > 20% and/or the coefficient of correlation (Rsq,adj) is <0.800 and/or the observation period over which the regression line is less than two-fold the resulting $t_{1/2}$ itself, rate constants and all derived parameters will be listed, flagged and included in the parameter outputs and descriptive statistics regardless of whether or not these criteria are met.

Partial area, AUC₀₋₂₄ should be calculated using the scheduled dosing interval, as defined in the protocol. The actual interval calculated from CRF time data should not be used.

CCI

CONFIDENTIAL
INFORMATION

CCI

CCI

63/66

Global Version ID: CCI

- Scatter plot of individual dose-normalized AUC_{0-24} , AUC_{0-t} , $AUC_{0-\infty}$, and C_{max} versus dose on a linear scale. A linear regression may also be overlaid.

The following listings, figures, and summary statistics of peposertib, its metabolite (*O*-demethylated product M467), and capecitabine and its metabolite (5-fluorouracil) PK concentration and parameter data will be provided:

[figure not shown]
- Listing of individual PK concentration data by scheduled time point, dose level, and fraction day
- Listing of individual PK parameters by dose level and fraction day
- Descriptive summary table of PK concentration data by scheduled time point, dose level, and fraction day
- Descriptive summary table of PK parameter data by dose level and fraction day
- Individual peposertib, M467, and capecitabine and 5-fluorouracil concentration-time profiles (linear and semi-logarithmic scales) will be plotted by dose level for each fraction day as spaghetti plots, using actual time points (where available).
- Arithmetic mean concentrations will be plotted on both linear ($\pm Sd$) and semi-logarithmic scales using scheduled time points – with all dose levels overlaid per fraction day, and with all fraction days overlaid per formulation dose level. Additional mean plots will be produced (on both linear [$\pm (Sd)$] and semi-log scale) to show the mean concentration-time data per dose level over the entire-time course. PK concentrations excluded from summary statistics will not be included in mean figures. Mean plots will only contain averages when $n > 2$.

All descriptive summaries of PK data will be performed using the PK analysis set.

[figure not shown]
Any PK concentrations or PK parameters excluded from PK evaluation or summary statistics will be included in subject listings and flagged; a reason for exclusion will be detailed in a footnote. Any flags should be included in the study specific SDTM and ADaM data sets. The Phoenix WinNonlin NCA Core Output will be provided in a separate listing.

CCI

CCI

CCI

16.4

Patient Reported Outcome

Not applicable for Phase Ib.

CCI

CCI

17**References**

Brookmeyer R and Crowley J. A confidence interval for the median survival time. *Biometrics* 1982;38:29-41.

Clopper CJ and Pearson ES. The use of confidence or fiducial limits illustrated in the case of the binomial. *Biometrika* 1934;26:404-13.

Kalbfleisch JD and Prentice RL. *The statistical analysis of failure time data*, New York: John Wiley & Sons 1980.

Mosteller RD. Simplified calculation of body-surface area. *N Eng J Med* 1987;317:1098.

18**Appendices****18.1****SMC SAP**

Refer to : [ctp-ms100036-0020-smc-iap-v1-26apr2019](#)

18.2**Clavien-Dindo classification**

Refer to : [Peposertib-Clavien_Dindo-Terms-v23_1.xlsx](#)

ELECTRONIC SIGNATURES

Document: ctp-ms100036-0020-iap-v3

Signed By	Event Name	Meaning of Signature	Server Date (dd-MMM-yyyy HH:mm 'GMT'Z)
PPD	Task Completed (Approval eSign): Approved	Business Approval	07-Jul-2021 16:38
PPD	Task Completed (Approval eSign): Approved	Technical Approval	08-Jul-2021 09:32
PPD	Task Completed (Approval eSign): Approved	Business Approval	08-Jul-2021 18:30

CCI

CCI

Global Version ID: CCI

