6.6.2.2 Capecitabine

Capecitabine is to be administered as recommended per current medical guidelines (NCCN 2019, Glynn-Jones 2017) for neoadjuvant treatment of locally advanced rectal cancer. The capecitabine dose is calculated according to body surface area.

Body surface area should be calculated based on established methods, e.g. the Mosteller formula (Mosteller 1987):

$$BSA (m^2) = \sqrt{\frac{Height (cm) \times Weight (kg)}{3600}}$$

Or in inches and pounds:

$$BSA (m^2) = \sqrt{\frac{Height (in) \times Weight (lbs)}{3131}}$$

If there is a change in body weight of at least 10% from baseline, the individual capecitabine doses should be recalculated. Otherwise the initial body surface area should be utilized for subsequent doses.

Capecitabine will be administered orally at a dose of 825 mg/m² twice daily 5 days a week throughout the RT course. The total daily dose, calculated in terms of mg/m², will be rounded to the nearest 500 mg, to allow for tablet size, and then divided into 2 doses. If this results in an uneven number of tablets (e.g. 7 tablets daily), then then the larger number will be taken with the morning dose (i.e. 4 tablets in the morning and 3 tablets in the evening). Capecitabine tablets are not to be split.

In addition, participants will be instructed to:

- Take capecitabine tablets in 2 daily doses: a morning dose and an evening dose
- Swallow capecitabine tablets with water within 30 min after a meal (breakfast and dinner).

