6.6.3.2 Capecitabine Management for Toxicities Other Than Diarrhea

Investigators must follow the package insert, the product information, the SmPC, and their site's specific policies/instructions for the final use of capecitabine.

Toxicity due to capecitabine administration may be managed by symptomatic treatment and/or modification of the dose (treatment interruption or dose reduction). Once the dose has been reduced, it should not be increased at a later time. For those toxicities considered by the treating physician to be unlikely to become serious or life-threatening, e.g. alopecia, altered taste, nail changes, treatment can be continued at the same dose without reduction or interruption. Participants taking capecitabine should be informed of the need to interrupt treatment immediately if moderate or severe toxicity occurs. Doses of capecitabine omitted for toxicity will not be replaced.

Hematological Toxicity

Participants with baseline neutrophil counts of $< 1.5 \times 10^9/L$ and/or platelet counts of $< 100 \times 10^9/L$ should not be treated with capecitabine. If these counts drop during treatment, doses of capecitabine are modified as shown in [Table 8](#).

Table 8 Dose Adjustment for Capecitabine for Absolute Neutrophil Count and/or Platelet Counts

Cell Count	Order of Occurrence	Action	Dose Resumed at (% of Starting Dose)
ANC $\geq 1.0 \times 10^9/L$ and platelets $\geq 75 \times 10^9/L$		Maintain capecitabine dose	100%
ANC $< 1.0 \times 10^9/L$ and/or platelets $< 75 \times 10^9/L$	First occurrence	Interrupt treatment until ANC $\geq 1.0 \times 10^9/L$ and platelets $\geq 75 \times 10^9/L$	100%
ANC $< 1.0 \times 10^9/L$ and/or platelets $< 75 \times 10^9/L$	Second occurrence	Interrupt treatment until ANC $\geq 1.0 \times 10^9/L$ and platelets $\geq 75 \times 10^9/L$	75%
ANC $< 1.0 \times 10^9/L$ and/or platelets $< 75 \times 10^9/L$	Third occurrence	Interrupt treatment until ANC $\geq 1.0 \times 10^9/L$ and platelets $\geq 75 \times 10^9/L$	50%
ANC $< 1.0 \times 10^9/L$ and/or platelets $< 75 \times 10^9/L$	Fourth occurrence	Discontinue capecitabine treatment	Not applicable

ANC=absolute neutrophil count.

Nonhematological Toxicity

For nonhematological toxicity due to capecitabine, doses are to be modified in line with [Table 9](#).

Table 9 Dose Adjustment for Capecitabine According to Common Terminology Criteria of Adverse Events Version 5.0 – Nonhematological Toxicity

Order of Occurrence	Grade 2	Grade 3	Grade 4

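### Beyond capecitabine CL/f and Vz/f on FD1, no dose-normalised exposure is planned for capecitabine or 5-FU, although tablet rounding makes the sampled morning dose differ between participants

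*SAP*

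**What the plan says.** **Dosing.** Protocol 6.6.2.2 states: "Capecitabine will be administered orally at a dose of 825 mg/m² twice daily 5 days a week throughout the RT course". The total daily dose "will be rounded to the nearest 500 mg, to allow for tablet size, and then divided into 2 doses". If the tablet count is uneven, the larger part is taken in the morning ("i.e. 4 tablets in the morning and 3 tablets in the evening"), and "Capecitabine tablets are not to be split". Protocol Table 7 has the morning dose taken in the clinic on PK days, after the predose draw. Protocol Table 4 measures capecitabine and its metabolite in the same blood draws as peposertib. The sampled dose is therefore the morning dose. Tables 8 and 9 (section 6.6.3.2) allow capecitabine to be interrupted and resumed at 100%, 75% or 50%, and "Once the dose has been reduced, it should not be increased at a later time".

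**Analysis.** For peposertib and M467, SAP 16.1 lists Cmax, AUC0-t, AUC0-24 and AUC0-∞ each divided by dose. For capecitabine and 5-FU it says "The following PK parameters will be calculated from capecitabine and its metabolite (5-fluorouracil) plasma concentrations for FD1 and/or FD9 as indicated", and lists Cmax, tmax, tlast, AUC0-t, AUC0-∞, the extrapolated percentage and half-life. CL/f and Vz/f are added for capecitabine only, on FD1. The outputs for all these analytes include a "Descriptive summary table of PK parameter data by dose level and fraction day" and mean concentration plots with the dose levels overlaid. For peposertib and M467, Racc(AUC0-24) is "The accumulation factor to assess the increase in exposure from FD1 to FD9 during time 0 to 24 hours", taken as the raw FD9 value over the raw FD1 value. Racc(Cmax) is built the same way.

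**The concern.** Within a cohort every participant is assigned the same peposertib dose, and that drug receives dose-normalised parameters. Capecitabine, whose milligram dose differs between participants in the same cohort, does not. The columns of the capecitabine and 5-FU tables are peposertib dose levels, so a difference between columns will naturally be read against peposertib dose. Protocol 2.3 lists drug-drug interactions among the important potential risks, and Protocol 8.5 says the concentrations will be used to evaluate capecitabine PK. With a planned cohort size of 3, one participant on the other side of a rounding step can move a cohort mean, and nothing in those rows would show that dose was the cause.

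**Working it through.** **Inputs from the documents.** 825 mg/m² twice daily, so 1650 mg/m² per day; rounding of the daily total to 500 mg; odd tablet in the morning; cohort size 3 (Protocol 6.6.2.2 and 9.2).

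**Assumptions not in the documents.** BSA normally distributed, mean 1.8, 1.9 or 2.0 m², SD 0.15, 0.20 or 0.25 m², limited to 1.3–2.7 m² (nine scenarios); exposure proportional to dose; 500 mg tablets.

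**1. The protocol's own example.** At BSA 2.1 m²: 1650 × 2.1 = 3465 mg, rounded to 3500 mg, which is 7 tablets, 4 in the morning (2000 mg) and 3 in the evening (1500 mg). This agrees.

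**2. Rounding bands.** Tablets = round(1650 × BSA / 500); morning dose = half the tablets, rounded up, × 500 mg.

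| BSA (m²) | Daily (mg) | Morning (mg) | Evening (mg) |
|---|---|---|---|
| 1.364–1.667 | 2500 | 1500 | 1000 |
| 1.667–1.970 | 3000 | 1500 | 1500 |
| 1.970–2.273 | 3500 | 2000 | 1500 |
| 2.273–2.576 | 4000 | 2000 | 2000 |

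The morning step lies at 3250/1650 = 1.970 m².
- BSA 1.96: 3234 mg, rounded to 3000; morning 1500 mg; 1500/1.96 = 765 mg/m².
- BSA 1.97: 3250.5 mg, rounded to 3500; morning 2000 mg; 2000/1.97 = 1015 mg/m².

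The sampled dose rises by 2000/1500 = 1.33-fold. In 0.01 m² steps from 1.50 to 2.30 m², 765 and 1015 mg/m² are also the minimum and maximum.

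**3. What is already adjusted.** CL/f = Dose/AUC0-∞ is the reciprocal of AUC0-∞/Dose. With equal clearance it is the same at 1500 and 2000 mg, so it would show that a pure dosing difference is not a clearance change. It exists for capecitabine on FD1 only.

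**4. Size in a cohort of 3.** If k more participants than in the comparison cohort take 2000 rather than 1500 mg, the geometric mean shifts by (4/3)^(k/3): 1.10, 1.21 and 1.33 for k = 1, 2, 3. One participant at 75% on FD9 (before tablet rounding) gives 0.75^(1/3) = 0.91.

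**5. How often.** Simulating 200,000 pairs of cohorts of 3 per scenario, with clearance the same in all participants:
- 13–58% of participants take at least 2000 mg in the morning.
- Morning dose alone moves the geometric mean ratio beyond 1.09-fold in 48–69% of pairs, beyond 1.2-fold in 6–23%, and outside 0.80–1.25 in 0.5–10%.

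**6. Which divisor.** Take AUC = Dose/CL with CL proportional to BSA^p. The SD of log exposure due to dose and body size, over the nine scenarios, is:

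| p | Raw | Per mg | Per mg/m² |
|---|---|---|---|
| 0 | 0.098–0.156 | 0 | 0.076–0.138 |
| 0.5 | 0.080–0.114 | 0.038–0.069 | 0.038–0.069 |
| 1 | 0.081–0.094 | 0.076–0.138 | 0 |

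Dividing by mg/m² gives less spread than raw values in every scenario at each p. Dividing by mg is worse than raw in seven of nine scenarios at p = 1. At p = 1 the raw cohort ratio exceeds 1.2-fold in only about 0.5–1.5% of pairs.

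**7. Racc.** Raw Racc = (FD9 dose / FD1 dose) × the ratio of dose-normalised values. The two agree when the dose is unchanged.

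**The case against.** - **Capecitabine is already dose-adjusted.** In part. The SAP uses the actual administered dose, and FD1 CL/f and Vz/f reflect it. A reader might infer that the drug has no dose adjustment at all; that is wrong. CL/f does not cover 5-FU, Cmax, AUC0-t or FD9, and it rests on an AUC extrapolated from a 6-hour profile.
- **No interaction question is posed.** The visible PK objective concerns peposertib, no interaction analysis is visible, and all tests are exploratory. Objective rows and PK text next to the dose-normalised scatter plot are redacted. That plot includes AUC0-24, which is not a capecitabine parameter, so it reads as a peposertib plot. This limits the point to the interpretability of planned tables.
- **The 33% step is a worst-case pair.** Correct. It separates two individuals, not two cohorts. Table 7 also lists 150 mg tablets, and section 6.1 defers final use to labelling and site policy, so actual doses may be less coarse.
- **Reductions before FD9 are limited.** FD9 falls in Week 2. A 75% dose is possible, for example after a first Grade 3 event. A 50% dose needs a third hematologic or Grade 2 event, or a second Grade 3 event, each after recovery, and is close to unreachable by then.
- **Dividing by milligrams can add spread.** True if clearance scales with BSA: over 1.50–2.30 m², AUC/Dose would then vary 2.30/1.50 = 1.53-fold, against 1.33-fold for raw AUC. This changes the divisor and leaves the gap.
- **Peposertib doses rarely change.** Table 10 mostly resumes at the same dose, and intraparticipant escalation is barred. Section 6.6 does allow modification at physician discretion, and SAP 13 tabulates dose reductions. The Racc point is therefore secondary.
- **Listings exist.** Individual doses and PK parameters are listed, so a careful reader could reconstruct the cause. The summary tables would not show it.

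**Conclusion.** The gap is real and modest. The 1500-to-2000 mg step follows exactly from the protocol's rule, and the SAP lists no dose-normalised Cmax or AUC for capecitabine or 5-FU. The typical cohort shift of 10–21% corresponds to one or two more participants of three on the higher morning dose. It assumes dose-proportional exposure, 500 mg tablets, the assumed BSA range, and clearance unrelated to body size; it is smaller if clearance rises with BSA.

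A reader might go further and conclude that the plan will produce a false drug interaction, or that cohorts will differ by a third. The documents do not support either. No interaction test is visible, and rounding alone takes the ratio outside 0.80–1.25 in at most about 10% of simulated cohort pairs.

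**What to change.** In SAP 16.1, for capecitabine and 5-FU:
- Add Cmax and AUC0-t (FD1 and FD9), and AUC0-∞ where it is derived, divided by the actual morning capecitabine dose of that fraction day in mg/m². Use the BSA rule of SAP 13. Values per mg may be added as well.
- Keep the raw values.
- Show the actual morning dose (mg and mg/m²) beside the summaries by dose level.

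As a secondary change, compute Racc(Cmax) and Racc(AUC0-24) for peposertib and M467 from the dose-normalised values already derived.

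The cost is a few derived variables. Actual morning and evening doses are recorded on the administration eCRF pages, and BSA is already derived. No dosing change is implied.
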